2.5.3 Handling of intercurrent events

The primary analyses will account for intercurrent events as follows:

1. **Study discontinuation due to reasons other than death:** It is assumed that participants discontinuing the study prior to Week 52 would follow the same trend as participants who continued and remained in the study for the full 52 weeks. Data collected up to the point of discontinuation will be included in the MMRM (Hypothetical strategy).

2. **Use of prohibited concomitant medications not for the intent to treat SMA:**
Assessments collected while/after receiving prohibited concomitant medications not for the intent to treat SMA will be included in the analyses (Treatment policy strategy).
3. **Use of prohibited concomitant medications for the intent to treat SMA (i.e. nusinersen, risdiplam):** Assessments collected while/after receiving prohibited concomitant medications for the intent to treat SMA will not be included in the analyses. Only data collected up to the point of initiating a prohibited medication for the intent to treat SMA will be included in the MMRM and the data collected after the initiation of prohibited medication for the intent to treat SMA will be considered as missing (Hypothetical strategy).
4. **Study discontinuation due to death:** The worst HFMSE score will be imputed for participants who discontinue the study due to death, and this imputed score will be utilized in the analysis. The “worst score” refers to the worst (lowest) HFMSE score collected for the participant who had the death event throughout the trial (considering both the baseline and post-baseline period). It is anticipated that this intercurrent event is unlikely to occur during this study.

2.5.4 Handling of missing values not related to intercurrent event

The primary analysis method, MMRM, implicitly imputes missing data under a missing at random assumption.

2.5.5 Sensitivity analyses

In order to assess the potential impact of excluding participants from the primary analysis who are randomized into the study but did not receive treatment, the primary efficacy analysis will be repeated using the ITT Set.

In order to assess the potential impact of missing HFMSE data, sensitivity analyses will also be conducted using the FAS, where missing data will be imputed using multiple imputation (MI) methodology, if there are more than 5% of patients (≥ 7 participants) in the FAS missing end of follow-up period 1 HFMSE data. MI analysis with both the missing at random (MAR) and the missing not at random (MNAR) assumption will be performed. For MI with MNAR assumption, a tipping-point analysis will be performed using pattern-mixture model with a delta-adjusted pattern imputation. These specific imputation methods are further described in [Section 5.1.4](#) of this SAP.

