2.1.1 General definitions

Study treatment is OAV101 (1.2x10¹⁴ vector genomes) or sham administration.

The **date of first administration of study treatment** is defined as the date of OAV101/sham administration during Treatment Period 1.

The **date of second administration of study treatment** is defined as the date of OAV101/sham administration during Treatment Period 2.

Study day is the number of days since the date of first administration of study treatment for period 1 and number of days since the date of second administration of study treatment for period 2.

- Study day 1 is the date of the first administration of study treatment during Treatment Period 1 and the date of second administration of study treatment during Treatment Period 2 .
- Study day of date X = date X – date of first administration of study treatment during Treatment Period 1 + 1 if date X is on or after the date of first administration of study treatment during Treatment Period 1.
- Study day of date X = date X – date of first administration of study treatment during Treatment Period 1 if date X is before the date of first administration of study treatment during Treatment Period 1. Study days before the first study treatment administration during Treatment Period 1 will have the prefix “-”.

Baseline is defined as follows:

- **HFMSE**: Baseline value for HFMSE (i.e., total or individual item) score is defined as the average of HFMSE (i.e., total or individual item) score used for stratification (maximum of all available values before baseline visit) and the measurement or evaluation made at the baseline visit prior to the first administration of study treatment during Treatment Period 1, assuming both values have complete and valid scores available. If just one of the above mentioned values (score used for stratification and baseline visit measurement) has a complete and valid score available, then the baseline HFMSE (i.e., total or individual item) score is defined as the single available value.

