2.2 Analysis sets

The **Intent to Treat Analysis Set (ITT)** comprises all randomized participants, regardless of whether they were dosed with study treatment during Treatment Period 1. Participants will be analyzed according to the treatment/procedure they have been assigned to.

The **Full Analysis Set (FAS)** comprises all randomized participants who were dosed with study treatment during Treatment Period 1. Participants will be analyzed according to the treatment/procedure they have been assigned to.

As per the protocol, participant randomization occurs approximately 2 weeks prior to when treatment administration/sham procedure is planned to occur. There is a possibility that a participant is randomized but subsequently becomes ineligible for the trial during this time and ultimately would not be dosed with the study treatment or contribute to the post-treatment study assessments. In order to account for this possibility, the FAS will exclude participants who were randomized but were not dosed with the study treatment.

The **Active Treatment Period 2 Set (ATP2)** comprises all participants who were dosed with the study treatment during Treatment Period 2. Summaries of data using ATP2 will be based on actual treatment/treatment sequence.

The **OAV101 Treated Analysis Set (OAS)** comprises all randomized participants who were dosed with OAV101 treatment during Treatment Period 1 or 2. Participants will be analyzed according to the treatment/procedure they have been assigned to.

The **Safety Analysis Set (SAF)** includes all participants who were dosed with the study treatment during Treatment Period 1. Participants will be analyzed according to the study treatment/procedure received.

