2.5.2 Statistical hypothesis, model, and method of analysis

The aim is to estimate the treatment effect of IT OAV101 compared to the sham procedure, for the target population on the primary endpoint. The justification of the corresponding primary estimand is detailed in [Section 1.2.1](#) of this SAP.

The statistical hypothesis for the primary endpoint being tested is that there is no difference in the change from Baseline in HFMSE total score at the end of Follow-up Period 1 in the OAV101 treatment group compared to the sham procedure group.

Let p_j denote the change from Baseline in HFMSE total score at the end of Follow-up Period 1 for treatments j , $j=0, 1$ where:

- 0 corresponds to sham procedure
- 1 corresponds to OAV101

In statistical terms, $H_0: p_1=p_0$, $H_A: p_1 \neq p_0$, i.e.:

- H_0 : OAV101 is not different from sham procedure with respect to the change from Baseline in HFMSE total score at the end of Follow-up Period 1.
- H_A : OAV101 is different from sham procedure with respect to the change from Baseline in HFMSE total score at the end of Follow-up Period 1.

The primary efficacy endpoint variable will be analyzed using a linear mixed effects repeated measures model (MMRM) with the observed change from Baseline in HFMSE total score at all post-Baseline visits (through the end of Follow-up Period 1) as the dependent variable. The fixed effects will include treatment, scheduled visit, treatment by visit interaction, CCI [REDACTED]

[REDACTED]. The primary analysis will be based on the FAS. An unstructured covariance matrix will be used. LSMs for each treatment group, standard errors, and associated 95% confidence intervals (CIs), difference of LSMs compared to sham procedure group, and the associated 95% CI for the difference, as well as the two-sided p-values will be tabulated by visit. The null hypothesis will be rejected if the two-sided p-value for the LSM difference between the OAV101 arm and the sham procedure at the end of Follow-up Period 1 is less than the alpha level dictated by the sequential testing procedure ([Figure 2-1](#)).

A line plot will be produced to display the LSMs for each treatment group and associated 95% CIs at each visit through the end of Follow-up Period 1.

In case of non-convergence issues, the covariance matrix will be simplified and a compound symmetry (CS) matrix will be used instead of the originally planned unstructured covariance matrix.

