2.6.5 Sensitivity analyses

The same methodology for sensitivity of the primary endpoint will be applied to the secondary endpoints.

Additionally, another sensitivity analysis will be performed for the RULM secondary endpoints. The RULM has been validated in SMA patients 30 months of age to adults. Therefore, subjects whose age at screening visit 1 was < 30 months of age will be excluded from this analysis.

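### The ITT rerun of the primary MMRM cannot show the effect of excluding undosed participants, because without post-baseline data they add nothing to the model

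*SAP*

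**What the plan says.** SAP section 2.5.5 gives the purpose of the ITT analysis as judging the effect of excluding participants who were randomised but not treated. The method is one clause: "the primary efficacy analysis will be repeated using the ITT Set".

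The other relevant provisions are these:

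- **Analysis sets (SAP 2.2).** ITT is everyone randomised; FAS is everyone randomised and dosed in Treatment Period 1. Both analyse by assigned arm, so they differ only by the undosed. The SAP notes that a participant may lose eligibility in the roughly two weeks between randomisation and dosing and "ultimately would not be dosed with the study treatment or contribute to the post-treatment study assessments".
- **Model (SAP 2.5.2).** The primary analysis is an MMRM "with the observed change from Baseline in HFMSE total score at all post-Baseline visits" as the response. The SAP's covariate list is partly redacted; the protocol summary gives strata and pre-treatment score as covariates.
- **Missing data (SAP 2.5.4).** The MMRM "implicitly imputes missing data under a missing at random assumption". There is no explicit imputation in the primary analysis, with one exception in SAP 2.5.3: "The worst HFMSE score will be imputed for participants who discontinue the study due to death".
- **Multiple imputation (SAP 2.5.5).** These "sensitivity analyses will also be conducted using the FAS", and only when more than 5% of the FAS lack the endpoint.
- **Secondary endpoints (SAP 2.6.5).** "The same methodology for sensitivity of the primary endpoint will be applied to the secondary endpoints".

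**The concern.** The rerun is there to answer one question: would the result change if the undosed were counted? An MMRM learns only from participants who have at least one response. If the undosed have none, adding them to the dataset changes the participant count and nothing else that matters for the comparison.

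A clinical study report would then show matching ITT and FAS results, and a reader would naturally take this as evidence that the exclusion is harmless. It would be no such evidence. Nothing else in the visible text fills the gap, because multiple imputation and the tipping-point analysis are confined to the FAS. The same rerun is carried over to the secondary efficacy endpoints.

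**Working it through.** **1. The plan's own power figure.** Inputs from SAP section 3: difference 3, SD 5, 75 versus 50, two-sided 5%. SE = 5 × √(1/75 + 1/50) = 0.913, so the noncentrality is 3/0.913 = 3.29. Power is 90.8% by the normal approximation and 90.3% by the noncentral t. This matches the stated figure of approximately 90%.

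**2. The algebra.** Each participant enters the MMRM likelihood through X′V⁻¹X, X′V⁻¹y and log|V|, taken over that participant's observed responses. With no responses, all three contributions are zero. The treatment difference, its SE and its p-value therefore cannot change. Per-arm LS means could shift if the software averages the baseline covariate over all records; the difference between arms would not.

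**3. Numerical confirmation.** I simulated unstructured REML MMRMs with 75 versus 50 participants, four visits, SD 5, correlation 0.7 and five dosed dropouts. The undosed were in the OAV101 arm with no post-baseline data. One replicate each:

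| Undosed | FAS n / ITT n | Response rows, both sets | Estimate (SE), both sets |
|---|---|---|---|
| 1 | 124 / 125 | 488 | 3.7801 (0.8495) |
| 3 | 122 / 125 | 478 | 1.4255 (0.8815) |
| 5 | 120 / 125 | 469 | 3.7984 (1.0113) |

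These confirm an identity; they do not measure an effect. A second set of simulations placed the undosed in one or both arms (3+1, 6+4 and 12+0 for OAV101+sham) and set their baselines 10 points lower. The ITT-minus-FAS difference was again exactly 0. As a check that the model can respond, giving the undosed explicit no-effect scores moved the estimate, for example from 3.84 to 3.48 in the 3+1 case.

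**4. Exceptions, for a true 3-point effect.**

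- *Death of one undosed OAV101 participant.* With imputed change c and a sham mean change of zero, the difference is (74 × 3 + c)/75: 2.96 for c = 0 and 2.92 for c = −3. The SAP calls death unlikely.
- *Undosed participants who still attend.* Protocol sections 8 and 9.1.1 leave room for this. For five OAV101-arm attendees with control-like scores, I assumed 12 time points, a linear effect reaching 3, and either compound symmetry (0.5 or 0.8) or AR(1) 0.9. The expected estimate is 2.987–2.995 with Week 4 only, 2.969–2.981 with Weeks 4–12, 2.944–2.950 with Weeks 4–24, and 2.80 with full follow-up.

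The SAP does not say how an attendee's score would reach a visit. Study day is the "number of days since the date of first administration of study treatment for period 1" (SAP 2.1.1), and the windows in SAP 2.1.2 use that clock. SAP 5.1.2 fills in a missing or partial administration date but does not say that it covers a participant who had no administration.

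**5. Scale, as illustration only.** The documents do not give the number undosed. If k of 75 OAV101 participants are undosed and have control-like outcomes, the difference over all randomised is 3 × (75 − k)/75:

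| k | Difference | Power, 75 vs 50 |
|---|---|---|
| 0 | 3.00 | 90.3% |
| 1 | 2.96 | 89.6% |
| 3 | 2.88 | 87.9% |
| 5 | 2.80 | 86.1% |
| 7 | 2.72 | 84.0% |

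Undosed sham participants with control-like outcomes leave the difference unchanged.

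**6. Why a replacement needs a matched FAS comparator.** Over 150 replicates with 25 imputations, FAS multiple imputation with ANCOVA minus FAS MMRM had an SD of 0.044–0.053. That is at least as large as the mean shift of about 0.04 from one undosed participant, so a change of method could hide the effect. With the same imputed datasets analysed with and without the undosed (300 replicates), ITT minus FAS was −0.039 (SD 0.019), −0.118 (0.045) and −0.201 (0.072) for k = 1, 3 and 5.

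**The case against.** The strongest reply accepts the algebra and disputes its weight. SAP 2.2 speaks of a possibility and describes one route to being undosed; participants who attend or die would move the rerun. The number undosed may be zero, SAP section 4 says enrolment is complete, and one undosed participant shifts the effect by only about 0.04 under the assumption used here. SAP 2.3.1 already reports how many participants are in each set, so the gap between ITT and FAS is visible. Imputing the undosed from sham counts them as untreated, whereas the primary estimand takes a hypothetical view of discontinuation. One sentence stating that ITT equals FAS when the undosed have no data would be cheaper.

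Much of this is fair, and some of it stands. The identity is conditional on the SAP's own expectation, and the exceptions are real, though the attendance route lacks a visit rule. Counts of undosed participants do not show their effect on the estimate. The sham-based analysis does ask a different question and has to be labelled so; control-like outcomes are an assumption. The power column in step 5 also needs context. With five undosed, the FAS itself (70 versus 50) has 89.5% power, so the closer contrast is 89.5% against 86.1%, and a sensitivity analysis has no power target anyway. A clarifying sentence would remove the false reassurance, but the question posed in SAP 2.5.5 would remain unanswered.

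**Conclusion.** The concern holds. On the expectation stated in SAP 2.2, the ITT rerun reproduces the FAS difference, SE and p-value exactly, so it cannot assess the exclusion it is meant to assess. The departures are an undosed death or undosed attendance; the first is called unlikely and the second has no visit-assignment rule.

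The consequence is limited to interpretation of a sensitivity analysis, for the primary and the secondary efficacy endpoints. The primary test, its alpha and the planned power are untouched, and nothing follows if everyone was dosed. The illustrative dilution of 0.04 points per undosed OAV101 participant assumes control-like outcomes and is not an estimate of bias.

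Protocol sections 12.1 and 12.4.3 to 12.4.6 are not in the text available, so a further rule there cannot be excluded; SAP section 1 says that the SAP supersedes the protocol's statistical considerations. The correction should be made, but it does not threaten the primary conclusion.

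**What to change.** Amend SAP 2.5.5 so that, if at least one randomised participant is undosed in Treatment Period 1, the unmodified rerun is replaced as follows:

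1. Impute the end of Follow-up Period 1 score of undosed participants in both arms from the sham arm, as a reference-based step added to SAP 5.1.4.1. Impute dosed participants under MAR. Keep the death rule and any observed scores, and state how scores are assigned to visits when there is no administration date.
2. Analyse with the ANCOVA (or logistic) model and the pooling already in SAP 5.1.4.1.
3. Run the same MAR imputation and model on the FAS from the same imputed datasets, whether or not the 5% trigger is met, so that the contrast isolates the undosed.
4. Label the result a sensitivity/supplementary analysis that counts undosed participants as untreated, and report the number undosed by arm beside it.

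Keep the FAS MMRM as primary, and carry the change through SAP 2.6.5.

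The cost is SAP wording, one new imputation step, and one extra FAS imputation run when the 5% trigger is not met. The sensitivity estimate may come out slightly smaller than the primary one.

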1.1 Study design

This is a Phase III, multicenter, single dose (1.2×10^{14} vector genomes), randomized, sham-controlled, double-blind trial that investigates the safety, tolerability, and efficacy of OAV101 IT in treatment naive, sitting and never ambulatory Type 2 SMA patients ≥ 2 to < 18 years. Approximately 125 participants aged ≥ 2 to < 18 years will be recruited, with approximately 65 participants aged between ≥ 2 and < 5 years and approximately 60 participants aged between ≥ 5 and < 18 years.

Participants will be randomized in a 3:2 ratio to receive OAV101 (1.2×10^{14} vector genomes) by lumbar IT injection (N=~75) or to receive a sham procedure (N=~50). **CCI**

CCI The highest pre-treatment HFMSE score recorded at Screening Visit 1 or Screening Visit 2 will be used for the purposes of randomization stratification.

Treatment Period 1 consists of OAV101/sham administration with in-patient hospitalization on Study Day 1, Day 2, and Day 3 (optional). Treatment Period 1 is followed by a 52-week out-patient follow-up period (Follow-up Period 1; Week 1-52) for safety and efficacy assessments.

At the point each participant completes Follow-up Period 1, those who are eligible will subsequently enter Treatment Period 2. Entry into Treatment Period 2 will occur in a rolling, seamless fashion as participants complete Follow-up Period 1. In Treatment Period 2, eligible participants who received a sham procedure on Study Day 1 of Treatment Period 1 will be hospitalized to receive OAV101 on Week 52 +1 Day and participants who received OAV101 on Study Day 1 of Treatment Period 1 will be hospitalized to receive a sham procedure on Week 52 +1 Day. In-patient observation will continue on Week 52+2 Days and Week 52+3 Days (optional). Treatment Period 2 is followed by a 12-week follow-up period (Follow-up Period 2; Week 53-64) for safety and efficacy assessments. The total duration of the study is 64 weeks. At the end of the study, all participants who received OAV101 will be eligible to enroll in a long-term follow-up study (15 years) to monitor long-term safety and efficacy.

The primary analysis will be performed after all participants have completed Week 52 or discontinued prior to Week 52. A final analysis will be performed after all participants have completed Week 64 or discontinued prior to Week 64.

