2.5.6 Supplementary analyses

An additional supplementary analysis will be performed if the percentage of participants using prohibited concomitant medications for the intent to treat SMA (i.e., nusinersen and risdiplam) is more than 5% (≥ 7 participants) in FAS. The supplementary estimand will be similar to the primary estimand except that the treatment policy strategy will be used (instead of the hypothetical strategy) to handle the intercurrent event of use of prohibited concomitant medications for the intent to treat SMA.

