2.13 Interim analysis

No formal interim analysis is planned for this trial.

3 Sample size calculation

The sample size calculation is primarily based on the primary variable, change from Baseline in HFMSE total score.

CCI [REDACTED]

[REDACTED]

[REDACTED]

CCI

Assuming a true treatment difference in the change from Baseline in HFMSE of 3 points and a standard deviation of 5 points, a sample size of 125 participants (75 in the OAV101 treatment group and 50 in the sham procedure group) provides approximately 90% power that the primary analysis will be statistically significant at the two-sided 5% alpha level assuming a minimal number of participants prematurely withdraw from the study prior to Week 52. In addition, assuming a larger treatment difference in the change from Baseline in HFMSE total score of 5 points and the same standard deviation as anticipated in the overall study population (5 points) in the ≥ 2 to < 5 years old group, a sample size of 65 participants (39 in the OAV101 treatment group and 26 in the sham procedure group) could achieve $> 95\%$ power in this younger age group.

Because this is the first OAV101 clinical trial to include the RULM assessment, there are no historical data available upon which to base sample size calculations on.

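### The pooled 5% trigger can leave up to 12% of the sham arm without a treatment-policy or missing-data check, and the SAP names no denominator for the younger age group

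*SAP*

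**What the plan says.** SAP 2.5.5 makes the multiple-imputation (MI) analyses conditional. The missing-at-random version and the delta-adjusted tipping point are both run on the FAS only "if there are more than 5% of patients (≥ 7 participants) in the FAS missing end of follow-up period 1 HFMSE data". The repeat of the primary analysis in the ITT set, in the same section, is unconditional.

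SAP 2.5.6 adds a supplementary estimand that keeps scores collected after a child starts prohibited SMA medication. It is estimated only if the share of such children "is more than 5% (≥ 7 participants) in FAS".

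Both thresholds count the two arms together. The visible text gives no threshold by arm or by age group.

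For the secondary endpoints, SAP 2.6.5 says: "The same methodology for sensitivity of the primary endpoint will be applied to the secondary endpoints". SAP 2.6.6 plans no supplementary analysis for them. SAP 2.5.3 sets scores after the start of nusinersen or risdiplam to missing in the primary analysis. SAP 5.1.4.1 applies the tipping-point shifts to imputed OAV101 values and leaves the sham arm unshifted.

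**The concern.** The treatment difference is biased by what happens within an arm, not by the pooled number of affected children. Allocation is 3:2, so a given count weighs more heavily in sham than in OAV101. A pooled count can stay under the limit while one arm is well over 5%.

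The stakes are clearest for SMA therapy. The primary estimand removes scores after nusinersen or risdiplam begins. The analysis in SAP 2.5.6 is the only planned treatment comparison that would use them. If the count stops at 6, that comparison is not produced, whichever arm the children belong to.

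A second gap is in the younger group. SAP 2.6.5 extends the sensitivity rule to endpoints in children aged 2 to under 5 years. It does not say whether the percentage, the count of 7 or the whole-FAS condition decides.

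**Working it through.** **Inputs.** From SAP Section 3: "a sample size of 125 participants (75 in the OAV101 treatment group and 50 in the sham procedure group"), "a sample size of 65 participants (39 in the OAV101 treatment group and 26 in the sham procedure group") for the younger group, a difference of 3 points, SD 5 and two-sided alpha of 5%. The trigger is from SAP 2.5.5 and 2.5.6.

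**Plan's own figures first.**
- 5% of 125 = 6.25, so the smallest count above 5% is 7. 6/125 = 4.8% and 7/125 = 5.6%. The percentage and count forms agree for the planned FAS, and for any FAS of 120 to 139. At 119 or fewer, 6 children already exceed 5%.
- SE = 5 × √(1/75 + 1/50) = 0.913. Power for 3 points is 90.3% (t-based), which reproduces the stated figure of about 90%.

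**Largest count that triggers nothing: 6.**
- All in sham: 6/50 = 12.0%.
- All in OAV101: 6/75 = 8.0%.
- If 6 cases fell at random over 125 children, the chance that all are sham is 0.3%. The chance that at least 3 are sham (more than 5% of that arm) is 46%.

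**Size for SMA-therapy starters.** Let each of 6 sham children gain g points from the therapy. The values of g are assumptions; the documents give none. The sham mean under treatment policy rises by (6/50) × g, and the treatment difference falls by the same amount.

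| Assumed gain g | Fall in difference | Remaining from 3 points |
|---|---|---|
| 2 | 0.24 | 2.76 |
| 3 | 0.36 | 2.64 |
| 5 | 0.60 | 2.40 |

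Smallest significant difference = 1.979 × 0.913 = 1.81. Margin at an effect of 3 = 3 − 1.81 = 1.19. Every row stays above 1.81. An observed difference between 1.81 and 1.81 + 0.60 = 2.41 could cross the line when g = 5. The upper limit is 2.05 when g = 2 and 2.17 when g = 3.

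**Size for missing OAV101 values.** The largest shift listed in SAP 5.1.4.1 (5 points), applied to 6 OAV101 children, moves the difference by 6 × 5/75 = 0.40.

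**Younger group, three readings of SAP 2.6.5.**
- More than 5% of 65: 3.25, so 4 children (6.2%).
- Count of 7: 7/65 = 10.8%.
- Whole-FAS condition: no fixed percentage. Up to 6/65 = 9.2% could be missing without a trigger, or 6/26 = 23.1% of the younger sham children if all six are there.

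At 4 to 6 missing, the first two readings give opposite decisions.

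**The case against.** A pre-specified materiality threshold is a legitimate choice, and this one is coherent where it is defined. Both triggers refer to the FAS, and for 125 participants the two forms are the same rule. A reader might infer that the threshold contradicts itself, or that it is really 10.8% in the younger group. The text does not support that: 10.8% is one reading of a sentence that names no denominator. For the treatment-policy analysis no younger-group threshold exists at all, because SAP 2.6.6 plans no supplementary analysis there.

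A reader might also infer that 12% of the sham arm goes unexamined. That is too strong. The figure is a ceiling. The MMRM uses all scores up to the event under missing at random, and the ITT repeat always runs. Starters left with no usable Week 48 or Week 52 score plausibly also count towards the missing-data trigger, so six of them plus one dropout would launch the imputation analyses.

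Nor do the documents show that starts would cluster in sham. Families and evaluators are blinded, and the therapy is prohibited (Protocol 6.2.2). Using it in Period 1 bars entry to Treatment Period 2 (Protocol Section 3), where eligible sham children receive OAV101.

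All of this stands. What it leaves open is that neither the MMRM, the ITT repeat nor imputation uses the discarded scores. Low expected uptake makes the treatment-policy analysis cheap; it does not justify a threshold blind to arm. The SAP change history says the 2.5.6 analysis was added at the FDA's request. It does not say how the threshold was chosen, so no agreement on it can be assumed either way.

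**Conclusion.** The concern holds as a modest, inexpensive improvement. Because the triggers pool the arms, up to 6 of 50 sham children could start SMA therapy without any planned treatment comparison that uses their later scores. Under assumed gains of 2 to 5 points, the unreported treatment-policy difference would be 0.24 to 0.60 points lower. The top of that range is a third of the smallest significant difference (0.60/1.81 = 33%). It would not overturn a 3-point effect, and the documents do not support saying so. It could matter for an observed difference below about 2.4.

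For the younger group the finding is one of definition: SAP 2.6.5 does not say which threshold governs.

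The figures assume that the FAS equals the planned 75 and 50, that SD is 5, and that a two-sample comparison stands in for the MMRM. The conclusion rests on the unredacted text.

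**What to change.** For the primary endpoint, run the treatment-policy estimate, the imputation analysis and the tipping point whatever the pooled count.

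If a trigger is preferred, replace both with more than 5% affected in either arm of the set being analysed, and delete the count of 7. At planned sizes that means 3 of 50 sham or 4 of 75 OAV101. Apply the same per-arm rule to the sensitivity analyses of the secondary endpoints, which gives 2 of 26 sham or 2 of 39 OAV101 in the younger group. This also settles the denominator in SAP 2.6.5.

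A lower trigger alone does not stress missing sham values, because SAP 5.1.4.1 shifts only OAV101. For sham children who start SMA therapy, the treatment-policy estimate is the check that matters.

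The cost is a few extra runs of methods the SAP already specifies. They may be uninformative when very few values are affected: a 5-point shift on one OAV101 child moves that arm's mean by 5/75 = 0.07.
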